short, the test box reference microphone will be calibrated. The probe tube will be inserted 25-27 mm from the intertragal notch in order to ensure placement within approximately 2-5 mm from the eardrum. The foam insert will be placed in the ear canal and care will be taken not move the probe tube during insertion. The RECD transducer will be coupled to the foam insert and the real-ear response will be obtained. The difference between the HA-1 coupler and real ear response is the measured RECD. Clinical application of the proposed model assumes all necessary pre-fitting procedures (e.g. earmold impression, tubing length, RECD) are completed at this session.

Session 2: The Testbox Fitting 'Visit'. Within five business days of receipt of the replacement hearing aids, the testbox fitting 'visit' will occur. The participants will **not** be present during the fitting. The vent size of each hearing aid will be measured. For both groups, the BTE earmold/ITE hearing aid will be attached to the 0.4cc coupler with putty ensuring that the eartip is flush against the opening of coupler and the vent sealed, as is standard with this procedure. The right and left hearing aids will be programmed separately to the NAL-NL2 prescription generated from the Verifit 2 using the measured RECD from Session 1 of each ear. The derived REAR of the hearing aids will be verified to the 50-, 65-, and 75-dB SPL prescriptive targets generated by the Verifit 2 system using the speechmap stimulus. The criterion for an appropriate fitting would be ± 3 dB between the output and the prescriptive target from 250 Hz to the frequency in which the unaided threshold crossed the 65-dB SPL target. We will then apply the refined vent size correction factor we previously determined. The real ear aided response (REAR85) will be measured using an 85-dB SPL swept pure-tone to ensure that the maximum output of the hearing aids does not exceed the predicted uncomfortable loudness levels of the participant (feedback manager deactivated during this measurement only). The programming options will be optimized based on the information obtained on the intake form (Appendix). After programming and verification, the hearing aids will be mailed to the patient along with the manufacturer brochure and programming report from the manufacturer software. A signature will be required to accept the delivery and the delivery will be tracked.

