Study 1 Power Analysis. The primary outcome of interest is based on fitting accuracy of each ear (i.e., deviation of REAR from prescriptive target across frequency). A power analysis for a repeated measure ANOVA with an effect size $\eta^2 = 0.10$, power ($1-\beta$) = 0.80, and $\alpha = 0.05$ requires a sample size of 100 ears (total of 50 participants) over the two groups. A small effect size is expected, as a small effect size was found in the preliminary data ($\eta^2 = 0.10$). Considering 15% attrition, then 8 additional participants will be needed ($N = 58$) resulting in 29 participants per group.

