Study 1 Data Analysis Plan. A generalized linear model will be applied to examine fitting accuracy. This analysis will examine differences (in dB SPL) for in situ REAR (based on testbox fittings) across frequency between the groups relative to the prescription. Because it is expected that differences within the two ears of the same subject will be smaller than differences across subjects, inclusion of both ears in the same analysis may over inflate the statistical power. However, it is also of interest to ensure that all data are considered. Therefore, we propose to complete separate analyses for the left and right ear, even though we expect the pattern of results to be very similar for each ear. These analyses will determine (1) in situ REARs of the testbox fittings matched the prescription within each group, and (2) if there was an effect of fitting accuracy as a function of style. A generalized linear model will be conducted to compare the expected (from prescription) and actual aided SII within and between groups. Finally, separate mixed model repeated measures ANOVA will be applied to examine group differences among the outcome measure subscales (i.e., SADL subscales, IOI-HA items/subscales, and for the APHAB subscales) to examine differences in outcomes between groups and between current hearing aid fittings and the replacement testbox fittings. For the COSI, the percentage of 'better' and 'much better' responses and the average of the final ability will be calculated across goals and compared between groups via a paired-sample t-test. The subjective outcomes of replacement hearing aids (Session 3) from testbox fittings will also be compared to normative data for each group by comparing our mean, standard deviation, and sample size to those same variables from the published outcome respectively via a Welch test. This will inform whether our outcomes for testbox fittings of replacement hearing aids from each group were consistent with the published norms or not. For the IOI-HA, the IOI-HA norms from the VA ROES DALC database that contains over 100,000 IOI-HA records will be used. In the same fashion, we can select IOI-HA norms from ROES by based on degree of hearing loss and hearing aid style. A

logistic regression also will be conducted to examine if the proportion of responses differ between the groups on the specific telephone and exit survey items of interest.

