Study 2 Power Analysis. The sample size for this aim is based on having 12 monaural hearing aid fittings (3 manufacturers of 1 open RIC, 1 closed RIC, 1 open RITA, and 1 closed RITA) per participant (ears counterbalanced across participants such that odd-numbered subjects obtain fittings in the left ear and even numbered in the right ear). To ensure a wide range of RECDs and the expected variability in slit leak venting with closed domes, our target sample size is now 96 participants. See randomization Table in Appendix 6 in the grant application for details. For this single session study, we will account for 10% attrition due screen failure and thus will recruit an additional 10 participants for a total of N = 106.

Study 2 Data Analysis. The data from this study will not be analyzed in the usual manner as the purpose of this study is to develop correction factors for open and closed dome fittings of RIC and RITA style hearing aids from several manufacturers. First the frequency-specific gain deviations for each ear as a function of vent size will be calculated. Second, Linear and nonlinear modeling of these data with the goal of developing a best fit model of the relationship between physical vent size and the frequency specific change in gain. The model will also be adjusted as a function of hearing loss, if necessary, to account for cases when the model correction would erroneously lead to negative gain.

Study 3 Power Analysis. A power analysis based on the same expectations as Study 1 regarding fitting accuracy was conducted. For a mixed model repeated measure ANOVA with an effect size $\eta^2 = 0.10$, power $(1-\beta) = 0.80$, and $\alpha = 0.05$ requires a sample size of 100 ears (total of 50 participants) over the four groups, or 13 participants per group. A small effect size is expected, as a small effect size was found in the SPIRE data ($\eta^2 = 0.10$). Nonetheless, considering increased variability due to venting and to obtain robustness required by clinical standards, we will increase the sample size to achieve higher power of $(1-\beta) = 0.95$. This would bring the sample size of ears to 152, or 76 participants in total (19 per group). Considering 15% attrition, then 12 additional participants will be needed (N = 88) resulting in 22 participants per group.

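### The fitting-accuracy model names no correlation across frequencies within an ear and is not the repeated-measures model that was powered; the left/right split halves the number of ears per analysis

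*Combined protocol and SAP*

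**What the plan says.** The Study 1 Power Analysis defines the primary outcome as "fitting accuracy of each ear (i.e., deviation of REAR from prescriptive target across frequency"), so each ear yields several values. The same paragraph bases the sample size on a repeated-measures model: "A power analysis for a repeated measure ANOVA with an effect size" η² = 0.10, power 0.80 and α = 0.05, giving 100 ears from 50 participants in two groups. The Study 3 Power Analysis does likewise ("For a mixed model repeated measure ANOVA with an effect size" η² = 0.10) and reaches 152 ears from 76 participants in four groups at power 0.95.

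The Study 1 Data Analysis Plan names a different model: "A generalized linear model will be applied to examine fitting accuracy". It examines differences "across frequency between the groups relative to the prescription", and a generalized linear model is also named for expected versus actual aided SII. No clustering term is given for either. In the same paragraph, mixed-model repeated-measures ANOVA is named for the questionnaire subscales.

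On a person's two ears, the plan warns that "inclusion of both ears in the same analysis may over inflate the statistical power" and therefore analyses left and right ears separately. The Study 3 Data Analysis section adopts a similar plan for the real-ear variables and repeats the split.

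**The concern.** Deviations from target at neighbouring frequencies in one ear share the same ear canal, probe placement, coupling and programming, so they are likely to be positively correlated. A generalized linear model with no clustering term counts each frequency as new, independent information. The plan sees this problem between ears and acts on it, but gives no remedy for the same problem within an ear.

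The affected quantities answer the plan's two stated questions for Study 1: whether fittings match the prescription within each group, and whether accuracy depends on hearing-aid style. In Study 3 they carry the comparison of experimental with standard-of-care fittings. Because the power sections assume another model, the stated power also does not describe the planned analysis. Splitting by ear adds two difficulties: nothing says what is concluded if the ears disagree, and each analysis has half the ears that the power calculation counted.

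**Working it through.** **Inputs from the documents.** η² = 0.10, so f² = 0.10/0.90 = 0.111; α = 0.05; 100 ears/50 participants/2 groups (Study 1); 152 ears/76 participants/4 groups (Study 3); 15% attrition; separate left and right analyses.

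**Assumed, because not stated.** Number of analysed frequencies per ear, m = 4 to 8; within-ear correlation, ρ = 0.1 to 0.7.

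**1. The plan's own figures.** Attrition reproduces: 50 × 1.15 = 57.5, so 58; 76 × 1.15 = 87.4, so 88. The repeated-measures sample sizes cannot be reproduced, since the number of repeated levels and the correlation are not given. As a benchmark I used a one-way F test with noncentrality N·f² and ears as independent units:

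- Two groups: 73 ears suffice for power 0.80; 100 ears give 0.91.
- Four groups: 103 ears are needed for 0.80 and 159 for 0.95; 100 ears give 0.79 and 152 give 0.94.

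**2. Group effect averaged over frequency, independence assumed.** With one ear per person and exchangeable correlation, the true variance of an ear's mean exceeds the assumed one by D = 1 + (m − 1)ρ. The ratio of naive to true standard error is 1/√D, and the two-group type I error is 2[1 − Φ(1.96/√D)].

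Example, m = 8, ρ = 0.7: D = 1 + 7 × 0.7 = 5.9; √D = 2.43; 1.96/2.43 = 0.807; type I error 0.42.

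The simulation columns are null simulations of 2 × 25 participants, 4,000 runs per cell, fitting group by frequency with independent errors. AR(1) means correlation decaying with frequency distance, with ρ between neighbours.

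| m | ρ | D | naive/true SE | type I, formula | simulated, exchangeable | simulated, AR(1) |
|---|---|---|---|---|---|---|
| 4 | 0.1 | 1.3 | 0.88 | 0.086 | 0.086 | 0.072 |
| 4 | 0.3 | 1.9 | 0.73 | 0.155 | 0.166 | 0.118 |
| 4 | 0.5 | 2.5 | 0.63 | 0.215 | 0.225 | 0.161 |
| 4 | 0.7 | 3.1 | 0.57 | 0.266 | 0.252 | 0.227 |
| 8 | 0.1 | 1.7 | 0.77 | 0.133 | 0.130 | 0.068 |
| 8 | 0.3 | 3.1 | 0.57 | 0.266 | 0.258 | 0.130 |
| 8 | 0.5 | 4.5 | 0.47 | 0.356 | 0.353 | 0.214 |
| 8 | 0.7 | 5.9 | 0.41 | 0.420 | 0.420 | 0.317 |

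For Study 3 (4 × 19), the overall group test runs from 0.11 to 0.72 under exchangeable correlation and from 0.08 to 0.57 under AR(1). Reducing each ear to one mean before testing gives 0.044 to 0.057 in every cell.

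**3. Contrasts between frequencies.** Here the naive/true ratio is 1/√(1 − ρ): 1.05 at ρ = 0.1 and 1.83 at ρ = 0.7. Standard errors are too large. Simulated type I error for frequency and for group by frequency is at most 0.045, and close to zero at high ρ. Expected versus actual SII in the same ear behaves the same way if the two are positively correlated.

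**4. The ear split.** On the one-way benchmark, 50 ears in two groups give power 0.64 and 76 ears in four groups give 0.65, against 0.91 and 0.94 with the ear counts that were powered. Pooling recovers only part of this. With between-ear correlation r, n participants with two ears are worth 2n/(1 + r) independent ears: from 100 (r = 0) down to 50 (r = 1) in Study 1, and from 152 down to 76 in Study 3.

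**The case against.** The strongest reply is that independence is inferred from silence. The plan never says that frequencies are independent, and generalized linear model may be loose wording for a repeated-measures general linear model, which would agree with the power sections. That is possible, so the inflation is conditional on fitting the model as named. It does not settle the matter: the same paragraph uses a repeated-measures term for the questionnaires, and the statistician is still to be determined, so the two terms could reasonably be read as two models.

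Several stronger readings are tempting, and the documents do not support them:

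- *Correlation between ears is ignored.* It is not. The split leaves one ear per person in each analysis.
- *All error bars are too narrow.* Only those for means and group effects averaged over frequency are; frequency contrasts go the other way.
- *Three input levels make it worse, and a standard repeated-measures ANOVA would drop incomplete ears.* The 50, 65 and 75 dB levels and the person-specific upper limit ("the frequency in which the unaided threshold crossed the 65-dB SPL target") belong to the fitting criterion at Session 2. The analysed in situ REARs come from Session 3, where neither levels nor range are stated.
- *Narrow intervals make equivalence too easy in Study 3.* That requires an interval-based test with a margin, and none is stated. If equivalence were read from a non-significant difference, standard errors that are too small would make that conclusion harder to reach.
- *The split discards data.* Both ears are analysed. The cost is lower efficiency and two results to reconcile.

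**Conclusion.** The concern holds in a limited, conditional form and should be corrected before analysis. Two things are certain from the text: the primary outcome's model is named differently from the one powered, and nothing is specified for correlation across frequencies within an ear. If the model is fitted as named, the two-group type I error for the averaged effect is about 0.09 to 0.42 under exchangeable correlation and about 0.07 to 0.32 under decaying correlation. Both ranges rest on assumed values of m and ρ, which the documents do not give. The count of 50 or 76 ears per analysis follows directly from the plan; the power of about 0.64 to 0.65 rests on the one-way benchmark, because the powered repeated-measures model cannot be reconstructed.

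**What to change.** Replace the generalized linear model and the separate ear analyses with one linear mixed model per study:

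- Fixed effects: group, frequency and group by frequency, plus input level if more than one level is analysed.
- Random effects: participant, and ear within participant, with a stated correlation structure over frequency. A GEE or robust variance clustered on participant would also serve.
- Data: both ears and all analysed frequencies, with the frequency set and input levels listed in the SAP.
- Aided SII: the same clustering, with expected versus actual as a within-ear factor.

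Then restate the power section for this model, counting participants as the independent units and giving the assumed number of frequencies and the within-ear and between-ear correlations.

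The cost is SAP wording and slightly more modelling work in standard software. Intervals for group effects averaged over frequency will be wider than under independence. In return there is one answer per hypothesis, from a model of the kind that was powered.

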Study 3 will use a quasi-random design. Participants receiving replacement receiver in the canal (RIC) mini BTE hearing aids and will be randomly assigned to one of four groups based on hearing-aid coupling (open vs closed domes). The standard of care (SoC) group receiving open coupling (SoC-open) or closed coupling (SoC-closed) or the experimental group receiving the experimental (EXP) hearing aid service delivery approach (EXP-open or EXP-closed). The outcomes of the experimental fittings will be compared to the respective SoC fitting.

Risk/Benefit Assessment

The procedures used in the proposed study produce minimal risks. There are no known social, legal, physical, psychological, genetic or financial risks associated with participation. All participants in Study 1 or Study 3 will receive a standard, comprehensive hearing evaluation. Some participants may find this boring or may be frustrated when repeated words that might be difficult to hear or listen for soft beeps. This is a common clinical procedure that is not invasive. All participants in Study 1 or Study 3 will obtain a cognitive screening test. This screener may cause people to feel uncomfortable having to be asked to remember things or if they find the test difficult. All participants will receive in situ real-ear verification of hearing aid fitting(s). There may be slight discomfort during these measurements, but they should not be painful and they are routine, taking only a few minutes to complete for each ear.

Participants in Study 1 only will have earmold impressions made of their ears so custom replacement behind-the-ear and in-the-ear hearing aids can be ordered for each ear. There is a rare, but small chance of ear injury during this routine clinical procedure. All standard clinical safeguards associated with obtaining earmold impressions (otoscopy, use of otoblocks) will be used.

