Study 3 Data Analysis. We will use a similar data analysis plan as in Study 1 for real ear/fitting accuracy variables. This will determine if derived REARs from open-fit RECD-fittings will accurately meet prescriptive targets and expected aided audibility and if *in situ* REARs of RECD-fittings are equivalent to *in situ* REARs in SoC fittings of open-fit styles. For statistical reasons, we propose to complete separate analyses for the left and right REAR data as described in Experiment 1. For self-report data, a separate mixed model repeated measures ANOVA will be conducted to compare outcomes amongst the groups. This will determine if subjective self-report outcomes across a variety of domains differs as a function of fitting experience and open-fit style.

The data will be analyzed by the PI; her collaborator and co-investigator ([name]., at Vanderbilt University—coded data only) who also will develop the correction factors; and the statistical consultant at Duke University (to be determined). A copy of coded data only will be

stored on the Duke University Server. A copy of all electronic data will also be stored at VA on \\v06.med.va.gov\\dur\\Research\\Research\\[name].

Privacy, Confidentiality, and Information Security

1. Lists of Data Reviewed and/or Collected for Screening/Recruitment and Conduction of Study:

It will be obtained, used, and/or shared for this study includes:

Identifier(s)	Source(s) of Health Information
 Names	 Medical history & physical exam information
 All geographic subdivisions smaller than a State, including street address, city, county, precinct, and zip code. Describe: mailing address	 Photographs, videotapes, audiotapes, or digital or other images
 All elements of dates (except year) for dates directly related to an individual, including birth date, admission date, discharge date, visit or treatment dates, etc.; and all ages over 89, Describe: age, audiology treatment dates (hearing test dates, fitting dates)	 Biologic specimens (e.g., blood, tissue, urine, saliva). Describe:
 Telephone numbers	 Progress notes
 Fax numbers	 Diagnostic / Laboratory test results

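### Each primary fitting-accuracy question is answered twice, once per ear, with no rule for combining the ears or for what to conclude if they differ

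*Combined protocol and SAP*

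**What the plan says.** Under Data Analysis and Statistical Considerations, the Study 1 Power Analysis states: "The primary outcome of interest is based on fitting accuracy of each ear", meaning deviation of the REAR from target across frequency. It asks for 100 ears from 50 participants at η² = 0.10, power 0.80 and alpha 0.05. The Study 3 Power Analysis raises power to 0.95 and asks for 152 ears from 76 participants, 19 in each of four groups.

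The Study 1 Data Analysis Plan expects a person's two ears to be more alike than ears of different people. It warns that putting both in one analysis may overstate power, yet it wants all data used. Its answer is: "we propose to complete separate analyses for the left and right ear, even though we expect the pattern of results to be very similar". Each ear's analysis is to settle the same two questions: whether in situ REARs match the prescription within each group, and whether accuracy depends on style.

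Study 3 Data Analysis carries this over: "we propose to complete separate analyses for the left and right REAR data as described in Experiment 1". The Design section adds for Study 3: "The outcomes of the experimental fittings will be compared to the respective SoC fitting".

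Hypotheses 1a and 3a, under Purpose, are each stated once, for the fitting approach and not for an ear. None of these sections splits alpha between the ears, names a deciding ear, requires both ears, or says what follows if they differ.

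**The concern.** Two analyses of one question give one answer only if there is a rule for combining them. Expecting similar patterns is not such a rule, because two similar estimates can fall on either side of p = 0.05. If a difference in either ear counts, the false-difference rate rises above 5%. If both ears must show it, a real difference between groups is more easily missed, which matters in a project that hopes to show accuracy and equivalence. With no rule stated, the reading can be chosen after the results are seen.

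Splitting the ears also discards information. The sample size is counted in ears from both sides, but each planned analysis holds one ear per participant.

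**Working it through.** **Inputs from the plan.** Alpha 0.05; η² = 0.10; 100 ears from 50 participants (Study 1, two groups, so 25 per group in each ear's analysis); 152 ears from 76 participants (Study 3).

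**Assumed.** The left-right correlation ρ is not given; I use 0.5 to 0.9. Tests are treated as two-sided. For a simple group contrast, the two ears' test statistics have about the same correlation as the two ears' outcomes.

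**Step 1: the plan's own figure.** With η² = 0.10, f² = 0.10/0.90 = 0.111. A simple two-group F test reaches 80% power at N = 73 (74 balanced), and its power at 100 is 0.91, so this reading does not reproduce 100 ears. The figure does appear if 0.10 is read as Cohen's f with 7 repeated measurements correlated at 0.5: 99 (100 balanced) at power 0.80 and 151 (152 balanced) at 0.95. The 7 and the 0.5 are not in the documents, so I do not call the count wrong. What matters here is that it is in ears, and each planned analysis has 50 of 100 or 76 of 152.

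**Step 2: false difference, if either ear counts.** P(either) = 0.05 + 0.05 − P(both), with P(both) from the bivariate normal distribution.

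| ρ | P(both) | P(either) |
|---|---|---|
| 0 | 0.0025 | 0.0975 |
| 0.5 | 0.0093 | 0.0907 |
| 0.8 | 0.0219 | 0.0781 |
| 0.9 | 0.0296 | 0.0704 |
| 1 | 0.0500 | 0.0500 |

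Simulated t tests with 25 per group agree: 9.0%, 7.9% and 7.1% at ρ = 0.5, 0.8 and 0.9. A four-group F test with 19 per group, as in Study 3, gives 9.1%, 8.1% and 7.3%.

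**Step 3: one ear significant, the other not, when a difference exists.** With η² = 0.10 and 50 participants, the two-group test in one ear has power 0.637. P(exactly one) = 2 × (power − P(both)).

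| ρ | P(both) | P(exactly one) |
|---|---|---|
| 0.5 | 0.481 | 2 × (0.637 − 0.481) = 0.312 |
| 0.8 | 0.541 | 2 × (0.637 − 0.541) = 0.192 |
| 0.9 | 0.569 | 0.135 (from unrounded values) |

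Under the Cohen's f reading in step 1, per-ear power would be lower, 0.46. For comparison, at a per-ear power of 0.50 the disagreement rate is 33% at ρ = 0.5 and about 21% at ρ = 0.8.

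**Step 4: what one model recovers.** The interval for the ear-averaged contrast, relative to a single ear's, has width √((1 + ρ)/2). Two correlated ears from 50 people are worth 100/(1 + ρ) independent ears.

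| ρ | Width ratio | Narrower by | Effective ears | Power, ear average (one ear: 0.64) |
|---|---|---|---|---|
| 0.5 | 0.866 | 13% | 66.7 | 0.76 |
| 0.8 | 0.949 | 5% | 55.6 | 0.68 |
| 0.9 | 0.975 | 3% | 52.6 | 0.66 |

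The gain in precision is real but shrinks as the ears become more alike. The larger benefit is having a single answer.

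**The case against.** The strongest reply is that separate ears are a declared and reasoned choice: the outcome is defined per ear, and the split avoids treating correlated ears as independent. That reason is sound against naive pooling. It does not count against a model with a participant effect, and the plan already uses mixed-model repeated-measures ANOVA for the self-report outcomes.

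Several limits on the figures stand:

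- The 7% to 9% needs a rule that either ear counts, which the plan does not state. If both ears had to be significant, the false-difference rate would be 0.9% to 3.0% over the same correlations. If the plan's remark on similarity means that within-person variance is below between-person variance, ρ exceeds 0.5 and 9.1% is a ceiling.
- A reader might infer that a sound fitting method would be rejected that often. The documents do not support this. The rate is for a between-group contrast, whereas Hypothesis 1a concerns match to target within group, and a false style difference does not refute it.
- Hypothesis 3a claims equivalence, so the damaging error there is a false claim of equivalence. If equivalence were required in both ears, no alpha adjustment would be needed. The plan does not state that requirement.
- A reader might multiply the tests further, by the three input levels or by open and closed coupling. The three levels belong to the fitting step ("verified to the 50-, 65-, and 75-dB SPL prescriptive targets generated by the Verifit 2 system"), and no separate test per level is specified. Hypothesis 3a names open-fit styles only.
- A reader might picture the ears pointing in opposite directions. The calculation shows only that one ear can be significant while the other is not.

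It is also fair that a lone ear-averaged group contrast would be a poor replacement. Both styles could miss target equally, left and right errors could cancel, and a non-significant difference would not show equivalence. The fix allows for this.

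**Conclusion.** The concern holds as a missing decision rule with an available better method. Each primary fitting-accuracy question is analysed once per ear, 0.05 is the only alpha stated, and no conclusion is defined when the ears differ. The disagreement rate is the firmer of the two figures because it does not depend on an either-ear rule: about 13% to 31% for ρ from 0.9 down to 0.5, at η² = 0.10 with 50 participants in a simple two-group test. The 7% to 9% false-difference rate is conditional on that rule and applies to the between-group contrast. Both rest on an assumed correlation. The halving of ears per analysis follows directly from the plan's own counts. This should be changed before analysis, but it does not invalidate the study.

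**What to change.** Replace the separate left and right analyses with one mixed model per study that contains both ears, with group, ear and frequency as fixed factors, participant as a random effect, and frequency repeated within ear. The within-person correlation is then modelled instead of avoided. Take the ear-averaged estimates from that model for the questions the plan already asks:

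- **Study 1:** deviation from the prescriptive target within each group (Hypothesis 1a), and the BTE versus ITE contrast.
- **Study 3:** each experimental group against its respective SoC group, with the open-fit contrast primary, as Hypothesis 3a specifies. Judge it as the equivalence question stated under Study 3 Data Analysis, not by a non-significant difference. That needs a stated margin, which the section does not give.

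Report ear-specific estimates and the ear-by-group term as supportive, so that left and right errors that cancel on averaging can be seen.

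The cost is a change to the analysis wording, with no new data. The downside is small: an effect confined to one ear would appear only in the supportive results.
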